3.2. Final Analyses

The final planned primary analyses will be performed after the completion of the following sequential steps for a CDISC study:

1. All participants have completed the study as defined in the protocol.
2. All required database cleaning activities have been completed and final DBR has been declared by Data Management (DM).
3. System Independent (SI) data to Study Data Tabulation Model (SDTM) data conversion has completed by Conversion Service at final Source Data Lock (SDL).
4. Final DBF on final SDTM datasets has been declared by DM.

Note: Randomisation codes had already been distributed in interim analyses.

4. ANALYSIS POPULATIONS

Population	Definition / Criteria	Analyses Evaluated
All Subjects	
 • All participants for whom a record exist on the study database, including pre-screened subjects that sign the informed consent document but do not complete a screening procedure (i.e., pre-screening failures) • This population will be used for the summary of “study populations” as study disposition 	
 • Study Population
Screened	
 • All screened participants. • This population will be used for the summary of reasons for screening failures. 	
 • Study Population
Enrolled	
 • All participants who are found to be eligible for the study based on the screening examination result. • This population will be used for the summary tables required by EudraCT. 	
 • Study Population
Intent-To-Treat (ITT)	
 • All participants who take at least one dose of study treatment in the treatment period. Participants will be analyzed according to the treatment they actually received. • This population will be used for all safety and other analyses. 	
 • Safety • Study Population • Other

Refer to [Appendix 11](#): List of Data Displays which details the population used for each display.

4.1. Protocol Deviations

Important protocol deviations (including deviations related to study inclusion/exclusion criteria, conduct of the trial, patient management or patient assessment) will be summarised and listed.

Protocol deviations will be tracked by the study team throughout the conduct of the study in accordance with the Protocol Deviation Management Plan [1Aug2018 Version 3.0].

- Data will be reviewed prior to freezing the database to ensure all important deviations are captured and categorised on the protocol deviations dataset.
- Participants who received an incorrect treatment will be captured as an important protocol deviation. The incorrect treatment will be identified in eCRF (if “No” to the question “Did the subject receive the correct treatment?” then this participants will be regarded as having received an incorrect container).
- This dataset will be the basis for the summaries and listings of protocol deviations.

A separate listing of all inclusion/exclusion criteria deviations will also be provided. This will be based on data as recorded on the inclusion/exclusion page of the eCRF.

5. CONSIDERATIONS FOR DATA ANALYSES AND DATA HANDLING CONVENTIONS

5.1. Study Treatment & Sub-group Display Descriptors

5.1.1. Interim Analyses

In interim analyses, only data until 24 weeks after first treatment will be used. This means the data after switching medication will NOT be included. Therefore, description in data displays will be the same as description in RandAll NG.

Treatment Group Descriptions for Interim Analyses			
RandAll NG		Data Displays for Reporting	
Code	Description	Description	Order [1]
A	FF/UMEC/VI 100/62.5/25	FF/UMEC/VI 100/62.5/25	1
B	FF/UMEC/VI 200/62.5/25	FF/UMEC/VI 200/62.5/25	2

NOTES:

1. Order represents treatments being presented in TFL, as appropriate.

Treatment comparisons will not be displayed.

If a given subject has incorrect study treatment during all period, then this subject will be analysed according to the treatment which he/she received. However, since it is uncertain whether a given subject has incorrect study treatment during all period (for 52 weeks) as of the timing of interim analyses, all analysis will be according to the allocated dose for interim analyses.

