### 10.2. Populations for Analyses

For purposes of analysis, the following populations are defined:

Population	Description
Screened	All screened subjects. This population will be used for the summary of reasons for screening failures.
Enrolled	All subjects who are found to be eligible for the study based on the screening examination result. This population will be used for the summary tables required by EudraCT.
ITT	All subjects who take at least one dose of study treatment in the treatment period. Subjects will be analyzed according to the treatment they actually received. This population will be used for all safety and efficacy analyses.

EudraCT: European Drug Regulatory Authorities Clinical Trial, ITT: Intent to Treat

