2. SUMMARY OF KEY PROTOCOL INFORMATION

2.1. Changes to the Protocol Defined Statistical Analysis Plan

There were no changes or deviations to the originally planned statistical analysis specified in the protocol (Dated: 13/MAR/2017), amendment 1 (Dated:24/MAY/2017) or amendment 2 (Dated: 25/OCT/2017).

In order to comply with regulatory guidance where the protocol referred to “Subjects” the analysis plan refers to “Participants”, with the exception of displays and study populations.

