3. PLANNED ANALYSES

3.1. Interim Analyses

No statistical interim analysis requiring any hypothesis tests is planned. However, the data will be summarized when all participants (who have not withdrawn) have completed 24-week administration of IP during the treatment period and the CRF data up to Week 24 for all participants is locked. It will be used for a JNDA submission.

Data up to week 24 (specifically, data up to the date of visit 5 (week 24) or the date of withdrawal before week 24 visit for a given subject) will be used for outputs (i.e., tables/figures). The definition of the cut-off date for the interim analysis will be the date of Visit 5 (Week 24) for the last enrolled participant in this study. As for the AE data to be included in interim analyses, please also refer to the definition of AE assessment window ([11.3.2.1](#)).

The interim planned primary analyses will be performed after the completion of the following sequential steps for this Clinical Data Interchange Standards Consortium [CDISC] study:

1. All participants have completed the 24-week administration during treatment period (except for the premature withdrawals) as defined in the protocol.
2. All required database cleaning activities have been completed and interim DBR for the 24-week during treatment period has been declared by Data Management (DM).

3. System Independent (SI) data to Study Data Tabulation Model (SDTM) data conversion has been completed by Conversion Service Provider at interim Source Data Lock (SDL).
4. Randomisation codes have been distributed according to RandAll NG procedures
5. Interim Database freeze (DBF) on interim SDTM datasets has been declared by DM.

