- If a given subject is allocated to FF/UMEC/VI 100/62.5/25 at visit 2 and switched at visit 5 then this subject will be handled as FF/UMEC/VI 100/62.5/25 until the day before visit 5 (week 24 visit) and as FF/UMEC/VI 200/62.5/25 after the day of visit 5 (week 24 visit). This means AEs which occurred until the day before visit 5 (week 24 visit) will be summarized in FF/UMEC/VI 100/62.5/25 and AEs which occurred after the day of visit 5 (week 24 visit) will be summarized in FF/UMEC/VI 200/62.5/25.

Treatment comparisons will not be displayed.

If a given subject has incorrect study treatment during all period, then this subject will be analysed according to the treatment which he/she received. This will be identified as all answers will be “No” to the question “Did the subject receive the correct treatment?” for all visits on eCRF.

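### The interim tables group everyone by allocated strength for a reason tied to 52 weeks, although only data to Week 24 are used, so a participant given only the other strength would sit in the wrong JNDA column

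*SAP*

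**What the plan says.** Protocol section 10.2 defines the ITT population, used for all safety and efficacy analyses, with the rule "Subjects will be analyzed according to the treatment they actually received". SAP section 4 repeats it: "Participants will be analyzed according to the treatment they actually received". Neither makes an exception for the interim.

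SAP section 5.1.1 starts from the same principle for treatment wrong throughout: "If a given subject has incorrect study treatment during all period, then this subject will be analysed according to the treatment which he/she received". It then sets this aside for the interim, because treatment over the full 52 weeks is not yet known: "as of the timing of interim analyses, all analysis will be according to the allocated dose for interim analyses". The same section limits the data: "In interim analyses, only data until 24 weeks after first treatment will be used". SAP section 3.1 gives the purpose of the interim: "It will be used for a JNDA submission".

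For the final analysis, SAP section 5.1.2.2 and Example 3 in section 11.6.1 place a participant who was wrongly treated throughout under the strength received. SAP section 2.1 states: "There were no changes or deviations to the originally planned statistical analysis specified in the protocol".

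**The concern.** The reason and the rule cover different periods. What a participant receives after Week 24 cannot affect a table that stops at Week 24. For someone who withdrew before Week 24 nothing is left to learn: the whole treatment is known when the interim data are locked.

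If such a participant took only the other strength, then exposure, adverse events, laboratory values, vital signs and ECGs are all shown under a strength never taken. The interim has no other by-strength view that would put this right, because summaries by dose at AE onset are prepared only for the final analysis (SAP section 8.2; none is listed in section 11.11.5). The final rule then moves an early withdrawal who was wrong throughout to the other column, although no new treatment data have arisen, so the interim and final reports would disagree about the same person.

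**Working it through.** This is mainly a check of one rule against another. The arithmetic only shows what one misplaced participant is worth.

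**1. Planning figure.** Protocol section 10.1 plans 110 enrolled so that about 100 complete at about 10% drop-out. 110 × 0.90 = 99, and 100 / 0.90 = 111.1, rounded up to 112. The 110 is reproduced within rounding of the stated assumptions. It is used below only as the total.

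**2. The rules side by side.**

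| Source | Participant given only the other strength is placed under |
|---|---|
| Protocol 10.2; SAP 4 (ITT) | strength received |
| SAP 5.1.2.2; Example 3 in 11.6.1 (final) | strength received |
| SAP 5.1.1 (interim) | strength allocated |

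The third row cannot stand with the first unless an exception is declared, and section 2.1 declares none.

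**3. Is the needed information available at the interim?** The schedule of activities has product dispensed at Visits 2, 3 and 4 before Visit 5. SAP sections 4.1 and 5.1.2.2 describe an eCRF question on whether the correct treatment was received, evaluated over all visits. I assume that its answers up to Visit 5 are in the locked interim data. Under section 4.1 a negative answer means only that an incorrect container was received, so it does not by itself show which strength was taken. Interim Listing 4 (section 11.11.9) shows planned and actual treatments, so that information is also planned to be available.

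**4. Size.** SAP section 2.3 sets no target allocation ratio, so column sizes are assumed. Take one participant allocated 200/62.5/25 who receives only 100/62.5/25 in the window and has one AE that nobody else has:

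| Assumed n (100 / 200) | By allocated: 100; 200 | By received: 100; 200 | Total |
|---|---|---|---|
| 20 / 90 | 0/20; 1/90 = 1.11% | 1/21 = 4.76%; 0/89 | 1/110 = 0.91% |
| 30 / 80 | 0/30; 1/80 = 1.25% | 1/31 = 3.23%; 0/79 | 0.91% |
| 55 / 55 | 0/55; 1/55 = 1.82% | 1/56 = 1.79%; 0/54 | 0.91% |
| 80 / 30 | 0/80; 1/30 = 3.33% | 1/81 = 1.23%; 0/29 | 0.91% |

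Over columns of 20 to 90, one participant is worth 100/20 = 5.0 down to 100/90 = 1.1 percentage points.

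**5. A threshold effect.** Interim Table 2.8 shows AEs reaching 3% in any group. 1/33 = 3.03% reaches the cut-off and 1/34 = 2.94% does not. In a column of 33 or fewer, one participant's placement can decide whether an AE appears. In the 30/80 row it appears only when grouped by treatment received; in the 80/30 row, only when grouped by allocation.

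**The case against.** The interim rule is an open choice. Section 5.1.1 states the principle, names the exception and gives a reason. In this SAP, wrong treatment throughout is a 52-week status, so holding to allocation until that status is known is a convention one could defend. Protocol section 10.3.4 says only that the Week 24 data will be summarised and fixes no grouping. The triggering case is unlikely: a participant who reaches Week 24 would need wrong supply at three successive dispensings, under interactive supply management and with on-site dosing checked by a second staff member (Protocol sections 7.3 and 7.6). Incorrect treatment would also be visible in interim Table 1.6 and Listings 4 and 5.

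The points on rarity and visibility stand, and they limit the weight of the finding. They do not repair the tables, because a listing does not move events or exposure to the right column. Nor does disclosure make the 52-week reason fit a 24-week window.

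Four stronger readings are tempting, and the documents do not support them:

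- **That participants are known to be misplaced.** The documents give no count.
- **That a comparison of strengths is distorted.** No comparison is planned, and Protocol section 5.4 gives the purpose as mainly the overall safety of the combination.
- **That the effect can be judged against the pneumonia rates in Protocol section 3.3.1** (18.3 and 8.5 per 1000 patient-years for FF/VI 200/25 and 100/25, a gap of 9.8). With 55 participants for 24 weeks there are 55 × 24 / 52.18 = 25.3 person-years, so any single event is worth 1000 / 25.3, about 40 per 1000. That reflects the small sample, not this rule.
- **That analysing these participants by strength received restores the ITT wording in full.** It does not. Partly wrong treatment still follows allocation, as it already does in the final analysis (SAP section 8.2 and Examples 1 and 2 in section 11.6.1).

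**Conclusion.** The concern holds, with limited weight. The reason in section 5.1.1 does not support using allocated strength for participants whose treatment was wrong throughout the interim window, least of all for those who withdrew before Week 24. For them the rule gives a wrong by-strength result in the JNDA tables, departs from the ITT definition and from the SAP's principle for treatment wrong throughout, and is not declared in section 2.1.

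The effect is conditional on such a participant existing, which is probably rare. At an assumed 55 per column, one participant is about 1.8 percentage points; the range is 1.1 to 5.0 for columns of 90 down to 20. Total columns are unaffected. The conclusion assumes that actual treatment up to Week 24 is in the locked interim data.

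**What to change.** Replace the last sentence of SAP section 5.1.1 with text such as:

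> *At the interim, a participant whose eCRF record shows incorrect treatment at all dispensing visits before Visit 5 (or before withdrawal), and whose recorded actual treatment (as in Listing 4) was the other strength throughout, is analysed by the strength received; all others are analysed by allocated strength.*

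State in SAP Sections 4 and 2.1 that partly wrong treatment is analysed by allocated strength. Footnote any participant whose column differs between the interim and the final analysis.

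The cost is one replaced sentence, two short statements and a flag derived from two records already planned: the eCRF answer and the actual treatment. The downside is that a participant who is wrong to Week 24 and correct afterwards may change column at the final analysis. The footnote covers this, and each report then shows what was taken in the period it covers.

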5.1.2. Final Analyses

In final analyses, two approaches for summaries will be used depending on summary tables.

5.1.2.1. Analyses by dose group

In principle, description in data displays will follow the patterns taking the treatment switching into account. All final analyses will use these descriptions below, except for summaries for “AE analyses by dose at the time of onset of the AE”. This approach is based on both the allocated doses and status of treatment switch at Week 24. Note that the participants will be allocated to either FF/UMEC/VI 100/62.5/25 mcg or FF/UMEC/VI 200/62.5/25 mcg, and only the participants who are allocated to FF/UMEC/VI 100/62.5/25 mcg will be allowed to switch treatment to FF/UMEC/VI 200/62.5/25 mcg only at Week 24. Therefore, treatment descriptions will be three as below table.

In this approach, summaries for total (overall) will be also presented.

Treatment Group Descriptions for Final Analyses by dose group				
RandAll NG		Switched treatment at Week 24	Data Displays for Reporting	
Code	Description	Description	Description	Order [1]
A	FF/UMEC/VI 100/62.5/25	No (FF/UMEC/VI 100/62.5/25 after week 24 or discontinued this study by week 24)	Only FF/UMEC/VI 100/62.5/25	1
A	FF/UMEC/VI 100/62.5/25	Yes (Switched to FF/UMEC/VI 200/62.5/25 at week 24)	FF/UMEC/VI 100/62.5/25 to FF/UMEC/VI 200/62.5/25	2
B	FF/UMEC/VI 200/62.5/25	N/A (Switched treatment will not be acceptable)	Only FF/UMEC/VI 200/62.5/25	3

NOTES:

1. Order represents treatments being presented in TFL, as appropriate.

5.1.2.2. Analyses by dose the time of onset of the AE (by dose at AE)

“AE analyses by dose at the time of onset of the AE” will be planned in this study due to Japan regulatory authority requirement. In these analyses, the following descriptions will be used.

Treatment Group Descriptions for Final Analyses by dose at AE			
Dose at AE		Data Displays for Reporting	
	Description	Description	Order [1]
A	FF/UMEC/VI 100/62.5/25	FF/UMEC/VI 100/62.5/25	1
B	FF/UMEC/VI 200/62.5/25	FF/UMEC/VI 200/62.5/25	2

NOTES:

1. Order represents treatments being presented in TFL, as appropriate.

In “by dose at AE” approach, the following rule will be applied.

- If a given subject is allocated to FF/UMEC/VI 100/62.5/25 at visit 2 and not switched at visit 5 then this subject will be handled as FF/UMEC/VI 100/62.5/25.
- If a given subject is allocated to FF/UMEC/VI 200/62.5/25 at visit 2 then this subject will be handled as FF/UMEC/VI 200/62.5/25.
- If a given subject is allocated to FF/UMEC/VI 100/62.5/25 at visit 2 and switched at visit 5 then this subject will be handled as FF/UMEC/VI 100/62.5/25 until the day before visit 5 (week 24 visit) and as FF/UMEC/VI 200/62.5/25 after the day of visit 5 (week 24 visit). This means AEs which occurred until the day before visit 5 (week 24 visit) will be summarized in FF/UMEC/VI 100/62.5/25 and AEs which occurred after the day of visit 5 (week 24 visit) will be summarized in FF/UMEC/VI 200/62.5/25.

Treatment comparisons will not be displayed.

If a given subject has incorrect study treatment during all period, then this subject will be analysed according to the treatment which he/she received. This will be identified as all answers will be “No” to the question “Did the subject receive the correct treatment?” for all visits on eCRF.

5.2. Baseline Definitions

For all endpoints (except as noted in baseline definitions) the baseline value will be the latest pre-dose assessment with a non-missing value, including those from unscheduled visits. If time is not collected, Day 1 assessments (except any assessments from unscheduled visit at the same date as Day1) are assumed to be taken prior to first dose and used as baseline.

Unless otherwise stated, if baseline data is missing no derivation will be performed and baseline will be set to missing.

5.3. Multicentre Studies

In this multicentre local study, enrolment will be presented by investigative site.

5.4. Examination of Covariates, Other Strata and Subgroups

5.4.1. Covariates and Other Strata

Any covariates and other strata will not be used in descriptive summaries and statistical analyses.

Subgroup analyses will not be planned in this study.

5.5. Multiple Comparisons and Multiplicity

Since this study does not plan efficacy analyses, multiple comparisons and multiplicity will not be applied.

5.6. Other Considerations for Data Analyses and Data Handling Conventions

Other considerations for data analyses and data handling conventions are outlined in the appendices:

Section	Component
11.3	Appendix 3: Assessment Windows
11.4	Appendix 4: Study Phases and Treatment Emergent Adverse Events
11.5	Appendix 5: Data Display Standards & Handling Conventions
11.6	Appendix 6: Derived and Transformed Data
11.7	Appendix 7: Reporting Standards for Missing Data

6. STUDY POPULATION ANALYSES

6.1. Overview of Planned Study Population Analyses

The study population analyses will be based on the ITT population, unless otherwise specified.

Study population analyses including analyses of subject's disposition, protocol deviations, demographic and baseline characteristics, prior and concomitant medications, and exposure and treatment compliance will be based on GSK Core Data Standards.

Details of the planned displays are presented in [Appendix 11: List of Data Displays](#). All outputs unless specified otherwise will be produced for the interim analysis and final analysis.

6.1.1. Subject Disposition

The overall subject disposition as well as the reason for withdrawal will be summarized for the ITT population, including the number and percentage of participants in each dose group and total. In interim analysis, "completed" means completion of Visit 5 (Week 24 visit).

The number and percentage of participants who completed the study treatment as well as the number who stopped the study treatment prior to the end of the study will be summarized, along with the reasons for discontinuation of the study treatment.

The reasons for Screen Failure or Run-in Failure will be summarized for the Screened Population for interim analysis only. Listings of failures prior to treatment will be generated.

The number and percentage of participants in each dose group and total will be summarized by status (entered, completed or withdrawn) at each epoch (run-in period, treatment period and follow-up period). In interim analysis, “completed” means completion of Visit 5 (Week 24 visit).

Using All Subjects, the number of participants in each population (Screened, Enrolled, ITT) will be summarized by dose group and total.

The number and percentage of participants at each center and within each country will be summarized. Note that this study includes only Japan as country.

6.1.2. Protocol Deviation

The number and percentage of participants with important protocol deviations determined by the study team will also be summarized. Listing for important protocol deviations will be prepared as well.

Listing will be provided for inclusion / exclusion criteria deviation record.

6.1.3. Demographic and Baseline Characteristics

Each of the following types of data will be summarized by dose group and total:

- Demographic data (age, sex, ethnicity, weight, height, body mass index (BMI), race)
- Duration of asthma
- Asthma medical history questionnaire
- Smoking history (smoking status of non-smoker or former smoker, and pack years for former smokers)
- Exacerbation history
- Cardiovascular history / risk factors and family history of cardiovascular risk factors
- ACQ-6 scores at Visit 1
- Pulmonary function (FEV₁, FVC, %predicted FEV₁)

Note: % predicted FEV1 will be derived. See Section 11.6.2.

